The Role of Skin Care Regimen in Skin Health

NCT03497130

April 5, 2018

Date: 04/05/2018

Principal Investigator: [name], MD

Application Number: IRB00165140

JHM IRB - eForm A – Protocol

The Role of Skin Care Regimen in Skin Health

1. Abstract

Dry skin is not a disease entity but it is an important patient matter as it can significantly decrease a person's quality of life. Individuals with dry skin experience discomfort associated with itching, skin tightness, and irritation. The lack of proper hydration is one of the most apparent characteristics of dry skin, which is associated with erythema and scaling on the skin surface. Skin care products with moisturizing features have beneficial effects in the treatment of dry skin. The aim of our study is to evaluate the role of a regular skin care regimen comprising of a mild cleanser and moisturizer in improving dry skin and overall skin health.

This study will have a study population of up to 100 individuals over the age of 18. Each study participant will have up to 3 on-site visits within 4 weeks. Select participants will be asked to apply a mild cleanser and moisturizer daily for 2 weeks. To assess the effects of a regular skin care regimen, clinical evaluations, digital photography, and subject questionnaires will be obtained during the study.

2. Objectives

- The primary aim of the study is to evaluate the role of a regular skin care regimen comprising of a mild cleanser and moisturizer in improving dry skin and overall skin health.
- The secondary aim of the study is to assess quality of life improvement with a routine skin care regimen.

3. Background

Dry skin is a common phenomenon and can dramatically decrease a person's quality of life as well as contribute to a wide variety of skin diseases. Individuals with dry skin experience discomfort associated with itching, skin tightness, and irritation¹. The lack of proper hydration is one of the most apparent characteristics of dry skin, which is associated with erythema and scaling.² Dry skin is caused by the interaction of lifestyle and environmental factors. Hereditary factors and advanced age can also contribute to dry skin. The severity of dry skin is usually exacerbated by the frequent use of harsh cleansers, the lack of moisturization, and by cold, dry air^{3,4}.

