Recruitment: Individuals will be recruited from patient populations seen at the general dermatology clinics of Johns Hopkins Department of Dermatology or from patient populations participating in Johns Hopkins Cutaneous Translational Research Program (CTReP) research studies. Interested study participants will be evaluated after their routine clinical care visits. Participants will also be recruited from other patient populations at the Johns Hopkins Hospital through the use of flyers and online advertisements. Study procedures will be conducted at the Johns Hopkins CTReP office located at the Johns Hopkins Outpatient Center. Recruitment may include Johns Hopkins University employees or students, but these groups will not be specifically targeted for participation. Interested individuals will be interviewed to ascertain whether they meet the basic eligibility criteria to participate in the study. Once eligibility has been demonstrated, the potential subjects will be directed to make their first study appointment. We will recruit up to 100 participants over the age of 18 with dry, itchy skin and they will be split into 2 groups. Participants will be randomly assigned to skin care regimen group (approximately 75% of total enrolled) and control group (approximately 25% of total enrolled). All evaluation will be conducted similarly in both groups.

Visit 1

During the first scheduled appointment, the research protocol will be discussed with the subject, and documentation will be obtained of the subject's consent to participate in the study as well as the subject's agreement to be contacted about future research studies.

Once informed consent is obtained, individuals will undergo a washout period of one week in which they are asked to refrain from the use of all moisturizers on their skin. Participants will be supplied with a skin cleanser, Dove[®] Soap, to use during this period and application log. All applications should be reported in the application log by the participants.

During this visit, investigators will also perform clinical assessment, take photographs and administer subject questionnaires.

Visit 2 (Baseline):

Date: 04/05/2018

Principal Investigator: [name], MD

Application Number: IRB00165140

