All participants will return after the washout period. Participants in the skin care regimen group will receive Vaseline[®] Moisturizer, Dove[®] Soap, and application log. These participants will be asked to apply the Vaseline[®] Moisturizer twice a day and use Dove[®] Soap daily for 2 weeks. All applications should be reported in the application log by the participants. A demonstration and verbal instructions for how and where to apply the products will be provided to the subjects along with the application log for daily use. Individuals not in the skin care regimen group will continue with the provided Dove[®] Soap.

During this visit, investigators will perform clinical assessments, take photographs and administer subject questionnaires.

Visit 3 (day 14±2):

During this visit, investigators will perform clinical assessment, take photographs and administer subject questionnaires. Application logs will be returned.

Clinical assessment: Clinical assessments will be performed 1) to record baseline skin findings, 2) to evaluate skin status by visual scoring, and 3) to identify any occurrence of any adverse events.

Photography: Standardized digital photographs will be obtained by study staff using a digital camera and software under standard photographic conditions. Photograph files will be coded to remove personal identifiers and stored on a secure hard drive in CTReP.

- b. Study duration and number of study visits required of research participants.
The study consists of up to 3 on-site visits within 4 weeks. We will allow 1 year to complete the study.
- c. Blinding, including justification for blinding or not blinding the trial, if applicable.
NOT APPLICABLE
- d. Justification of why participants will not receive routine care or will have current therapy stopped.
NOT APPLICABLE
- e. Justification for inclusion of a placebo or non-treatment group.
NOT APPLICABLE
- f. Definition of treatment failure or participant removal criteria.

Any clinical findings determined by the Investigator to be important and/or unusual will be referred to as an adverse event (AE). Study participants will be asked to contact clinic staff immediately if they experience an adverse reaction to the products at any time during the study.

Date: 04/05/2018

Principal Investigator: [name], MD

Application Number: IRB00165140

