Analysis will include paired and unpaired t-tests with two-tailed p-values. Values obtained at baseline, in middle of the study and after completing the study will be compared. The difference of measure values will be compared between application group and control group.
- d. Early stopping rules.
If the participant wishes to withdraw from the study for any reason, or if the primary caretaker or study investigators wish to cease use of the products.

8. Risks

The moisturizing lotion and wash are generally very well tolerated. Rarely, they can induce a burning sensation, dryness, skin irritation, erythema, stinging, sensitization, and dermatitis. Possible side effects from the product applications include irritant and allergic reactions. Irritation from these agents can be improved or relieved when participants stop using the products. Risk events, problems, and deviations will be reported by the PI directly to the IRB.

In terms of confidentiality, there are minimal risks as all study participant information will be de-identified. No confidential or protected information would be taken beyond the standard. There is a slight financial risk to the participants in the rare event that the above complications occur, requiring additional medical care.

9. Benefits

Date: 04/05/2018

Principal Investigator: [name], MD

Application Number: IRB00165140

Patients with dry skin in the skin care regimen group may experience improvement in their overall skin health. There will be no direct benefit to the participants in the control group. In addition, there is also the potential benefit to society at large. We hope to assess the role of a routine skin care regimen in improving dry skin and reducing symptoms. This can improve quality of life for patients who suffer from dry skin.

10. Payment and Remuneration

Study participants who undergo all study procedures, including correct application of moisturizing lotion and wash in the skin care regimen group will receive a total of \$60 at completion of the study.

11. Costs

Study costs will be covered by the UniLever Corp.

12. References

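### Items 4d and 4e are marked not applicable despite a moisturizer washout and a cleanser-only control arm, and the between-visit reporting wording covers only product reactions, so worsening off moisturizer is captured unreliably

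*Combined protocol and SAP*

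**What the plan says.** **Design (Section 4a).** After consent at Visit 1, "individuals will undergo a washout period of one week in which they are asked to refrain from the use of all moisturizers on their skin". A cleanser is supplied for that week. At Visit 2 the regimen group (about 75% of those enrolled) receives moisturizer and cleanser. For the rest the text reads "Individuals not in the skin care regimen group will continue with the provided" cleanser. Visit 3 is at day 14±2.

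**Justification items.** Section 4d, "Justification of why participants will not receive routine care or will have current therapy stopped", and Section 4e, "Justification for inclusion of a placebo or non-treatment group", are both answered as not applicable.

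**Expected effect and risks.** Section 3 states: "The severity of dry skin is usually exacerbated by the frequent use of harsh cleansers, the lack of moisturization, and by cold, dry air". Section 5 admits only people whose skin is already dry and itchy. Section 8 deals with the lotion and wash: "Possible side effects from the product applications include irritant and allergic reactions". Its other entries are confidentiality and a slight financial risk tied to those same complications. Section 9 says of controls: "There will be no direct benefit to the participants in the control group".

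**Recording of harms.** Section 4f defines an adverse event broadly, as whatever clinical finding the investigator considers important or unusual. The same item asks participants to contact the clinic at once about adverse reactions to the products, and says that such reactions may be entered in a problem events log. Section 7b makes adverse effects reported by participants and by the investigator the secondary outcome.

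**The concern.** The protocol asks people with dry, itchy skin to go without moisturizer and randomises about a quarter of them to an arm that is given none. It then marks as not applicable the two items meant to explain exactly that. Its own background gives a reason to expect some of these people to get worse, and its risk section does not mention the possibility.

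The statistical stake is how harms are ascertained. The secondary outcome depends partly on what participants report, and the one reporting instruction they are given concerns reactions to products. Worsening caused by the absence of a product does not fit that description. If it is reported less readily than irritation from a product, a comparison of adverse effects by arm is tilted, and the cost of the washout is not visible. A reader weighing Section 8 against Section 9 also sees an arm with no direct benefit and no stated physical risk other than reactions to the wash.

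**Working it through.** The documents give no figure to reproduce: the sample size of up to 100 comes without alpha, power, effect size or standard deviation. The check is mainly a comparison of sections, with some arithmetic for scale.

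**1. Justification items against design.** Item 4d asks about stopping current therapy; Visit 1 stops all moisturizers. Item 4e asks about a non-treatment group; Visit 2 creates a randomised group with no moisturizer supplied. One could argue that a moisturizer is not therapy, which would weaken the conflict at 4d. The conflict at 4e would remain.

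**2. Background against risks.** Section 3 lists lack of moisturization among the usual causes of worsening. In Section 8 dryness appears only as something the products can induce, and the only relief mentioned is stopping them. Going without moisturizer is not covered.

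**3. Routes by which worsening could be recorded.**
- *At a visit:* yes. The adverse-event definition is not limited to products, clinical assessments look for any adverse event, and Section 4a says that evaluation is similar in both groups. But there is no criterion for worsening, and worsening that the background describes as usual may not strike the investigator as unusual.
- *Between visits:* the contact instruction and the log refer to product reactions only.
- *As a score:* clinical assessments and questionnaires are done at Visits 1, 2 and 3. Visit 2 is labelled baseline, while Section 7c compares baseline, middle and end, so it is unclear whether the Visit 1 to Visit 2 change will be analysed.

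**4. Why capture may differ by arm.** During washout everyone is on cleanser alone, so under-reporting there need not differ by arm. After Visit 2 the regimen group has a newly supplied product to which a skin change can be attributed. Controls have only the cleanser they were already using. An instruction framed around product reactions is therefore likelier to prompt a call in the regimen group.

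**5. Scale.** Inputs: at most 100 participants, about 75 regimen and 25 control (Section 4a); washout of 7 days; Visit 3 at day 14±2, taken as counted from Visit 2 (assumption).
- Days off moisturizer, everyone: 7.
- Days off moisturizer, controls, if they use none of their own after washout: 7 + 12 = 19 to 7 + 16 = 23.
- Person-days off moisturizer on the same condition: 100×7 + 25×14 = 700 + 350 = 1,050. Person-days on it: 75×14 = 1,050.
- If no worsening were recorded, the exact one-sided 95% upper bound on the true rate is 1 − 0.05^(1/n). For n = 25 this is 11.3%; for n = 100 it is 3.0%. These bounds assume complete capture, so with incomplete capture a zero count would be weaker evidence still.

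**The case against.** The strongest reply is that the safety data are not blind to this harm. The adverse-event definition is broad and applies in both arms, visits look for any adverse event, and all problem events go to the IRB. Controls also use a study product: Section 8 covers the wash, and dryness is among its listed effects, so a control could report dryness as a reaction to it. Worsening is in any case measured by the primary-outcome scores. Section 7d allows withdrawal for any reason and 4f lets the investigator remove a participant, so stopping the products is not the only way out. The contact instruction may be a minimum, and consent pages are not in the public file. Prior moisturizer use is not required for entry, so the number who actually stop anything is unknown, and the cleanser supplied is regarded as mild, so net worsening is plausible but not certain.

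Much of this stands. A reader might infer that worsening off moisturizer is never counted as a harm, or that the safety comparison counts the harms of one arm only. The documents do not support that: recording is discretionary, not absent. Nor do they say that controls must avoid their own moisturizer after washout; they say only that none is supplied.

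The reply does not remove the contradiction in 4d and 4e or the silence in Section 8. It also leaves the mismatch within 4f between a broad definition and a product-bound reporting instruction. Scores taken at visits do not replace event reports between visits.

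**Conclusion.** The point holds in a limited form. Sections 4d and 4e contradict the washout and the control arm and must be reconciled with Sections 3, 8 and 9. Section 8 omits a physical harm that Section 3 makes foreseeable. Worsening off moisturizer can be recorded at visits at the investigator's discretion, but its capture between visits is unreliable and may differ by arm.

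The size of any bias cannot be estimated, because the documents give no rate for worsening or for product reactions. What can be stated is exposure: 7 days off moisturizer for up to 100 people, and 19 to 23 days for about 25 controls. The longer figure depends on controls using none of their own after washout and on day 14 being counted from Visit 2. The primary comparison and its tests are unaffected. This is an inexpensive improvement to safety reporting that should be made; it is not a flaw that undermines the trial.

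**What to change.** 1. Reconcile 4d and 4e with the moisturizer stop at Visit 1 and the cleanser-only control arm, and with Sections 3, 8 and 9. State whether controls may use their own moisturizer after washout, since the text is silent.
2. Address in Section 8 the possibility of worsening dryness or itch while off moisturizer.
3. Reconcile the reporting wording in 4f with the broader adverse-event definition in the same item, so that reporting of skin worsening does not depend on blaming a product. This should hold in both arms and during washout.
4. Tabulate by arm, descriptively, the change in the existing visual and questionnaire scores from Visit 1 to Visit 2 and from Visit 2 to Visit 3, with the number worsening by an amount stated in advance. The amount matters: on a continuous score with no true change, about half would worsen by chance.

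The cost is protocol wording and one table from data already collected, with no new visits, measurements or participants. The downside is small: the adverse-effect count will rise, probably mostly in the washout and among controls. How a participant who worsens is managed is for the investigator to reconcile across the sections; no clinical rule is proposed here.

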Such reactions may be documented in a problem events log. The Investigator will use her discretion to remove participants from the study, and all problem events will be reported to IRB.

- g. Description of what happens to participants receiving therapy when study ends or if a participant's participation in the study ends prematurely.
NOT APPLICABLE

5. Inclusion/Exclusion Criteria

Inclusion:

1. Participants must be over the age of 18 years old with dry, itchy skin;
2. Participant must be willing to comply with the requirements of the protocol;
3. Participant must have the ability to understand and communicate with the investigator;
4. Participant must provide informed consent.

Exclusion:

1. Subjects who are unable to provide informed consent;
2. Subjects who are unable to refrain from swimming or hot tub use or no more than 2 showers per day throughout the study duration
3. Subject with significant medical history or current skin diseases that the investigator feels is not safe for study participation;
4. Subjects who have been treated with systemic retinoids or steroids within the past month prior to entry to the study;
5. Subjects who have been treated with topical steroids, retinoids or other topical drugs within 2 weeks prior to entry to the study;
6. Recently treated or current skin diseases that would affect clinical evaluation;
7. Subjects who self-report that they are pregnant or nursing;
8. Patients with history of investigational drug use in the 30 days prior to entry into the study.

6. Drugs/ Substances/ Devices

- a. The rationale for choosing the drug and dose or for choosing the device to be used.

NOT APPLICABLE

- b. Justification and safety information if FDA approved drugs will be administered for non-FDA approved indications or if doses or routes of administration or participant populations are changed.

NOT APPLICABLE

Date: 04/05/2018

Principal Investigator: [name], MD

Application Number: IRB00165140

- c. Justification and safety information if non-FDA approved drugs without an IND will be administered

NOT APPLICABLE

7. Study Statistics

- a. Primary outcome variable.
Clinical/visual scores and subjective score from subject questionnaires.
- b. Secondary outcome variables.
Adverse effects reported by participants and investigator.
- c. Statistical plan including sample size justification and interim data analysis.

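### Adverse effects are the only secondary outcome variable, but section 4f makes logging of participant-reported reactions permissive and leaves the definition of an adverse event to investigator judgement

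*Combined protocol and SAP*

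**What the plan says.** Section 7b gives the secondary outcome as "Adverse effects reported by participants and investigator". No other secondary outcome variable is listed.

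Section 4f supplies the rules for collecting it:

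- Investigator source: "Any clinical findings determined by the Investigator to be important and/or unusual will be referred to as an adverse event (AE". No criteria, severity grade or causality scale accompany this.
- Participant source: "Study participants will be asked to contact clinic staff immediately if they experience an adverse reaction to the products at any time during the study".
- Recording of the participant source: "Such reactions may be documented in a problem events log".

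Three other places bear on the point. Section 4a makes the detection of adverse events one of three purposes of the clinical assessment, which takes place at all three visits, and says evaluation is similar in both groups. Sections 4f and 8 require problem events, risk events, problems and deviations to go to the IRB. Section 8 describes the expected product reactions: "Rarely, they can induce a burning sensation, dryness, skin irritation, erythema, stinging, sensitization, and dermatitis".

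**The concern.** An outcome variable needs a rule that says what counts and that it must be written down. Here the rule for one source is permissive, and the rule for the other is a personal judgement without criteria, made by someone whom the plan does not blind. Two investigators could follow section 4f exactly and produce different counts from the same participants.

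The reactions most exposed are the mild, foreseeable ones. Those are also the ones that matter most for a soap and a moisturizer, for which serious events are not the main expectation. If the record shows few or no adverse effects, a reader could not tell whether few occurred or few were written down.

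**Working it through.** No arithmetic settles this, so the provisions are followed from outcome to record.

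1. **Outcome.** Section 7b needs data from participants and from the investigator.

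2. **Investigator source.** Section 4a has the clinical assessment look for adverse events without restriction. The only definition of an adverse event is in section 4f, and it admits a finding only if judged important or unusual. The visit check inherits that filter. Example: faint erythema at Visit 3 in a regimen user. Section 8 already names erythema as a known reaction, so an investigator could reasonably consider it neither important nor unusual and not record it. Another could point out that section 8 calls such reactions rare, consider it unusual, and record it. Both comply.

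3. **Participant source.** The request to contact staff has no severity threshold, so the importance filter does not apply here. The weak link comes afterwards, because a log entry is allowed but not required. Example: a participant telephones about stinging on day 5. Stinging is a symptom that may leave nothing to see, and it may have gone by Visit 3. If the call is not logged, no stated provision puts it into the outcome data. The questionnaires might pick it up, but their content is not described.

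4. **IRB reporting.** Sections 4f and 8 make this mandatory, but for categories that are not defined. It is an oversight channel, and nothing says that what is sent becomes study data.

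5. **Analysis.** Section 7c names paired and unpaired t-tests. It gives no summary or comparison for adverse effects, so the analysis plan does not imply a recording format either.

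6. **Size.** The inputs would be a true reaction rate *p* and the share of reactions recorded. The documents give neither. To show how far any figure depends on them, take the regimen group at its maximum of about 0.75 × 100 = 75 and assume, purely for illustration, that half of reactions go unrecorded. The chance that the record shows no reactions is (1 − *p*)^75 with full recording and (1 − *p*/2)^75 with half:

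| Assumed *p* | Full recording | Half recorded |
|---|---|---|
| 1% | 0.99^75 = 47% | 0.995^75 = 69% |
| 5% | 0.95^75 = 2% | 0.975^75 = 15% |
| 10% | 0.90^75 = 0.04% | 0.95^75 = 2% |

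The answer moves so much with *p* that no single row can stand as the size of the problem.

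**The case against.** The strongest reply is that section 4f is not the whole system. Adverse events are actively looked for at each visit and in both groups, participants may report any product reaction however mild, and IRB reporting is mandatory. This is right as far as it goes, and it limits the point. A reader might infer that recording of adverse effects is optional throughout. It is not: the permissive wording governs one log, for reactions that participants report. What remains is that the visit check borrows the section 4f definition and that IRB reporting does not create outcome data.

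Three stronger readings are tempting and are not supported:

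- *Worsening in controls from going without moisturizer cannot be counted.* Section 3 does say that dry skin is "exacerbated by the frequent use of harsh cleansers, the lack of moisturization, and by cold, dry air", and the prompt to participants is limited to reactions to the products. But the section 4f definition of an adverse event is not tied to product use, so worsening in a control can qualify. Visual scores and questionnaires, the primary outcome under section 7a, also measure it in both groups. Whether section 8 should disclose that risk is a separate matter.
- *The comparison between arms is distorted because regimen users have an extra product to react to.* More reactions from an added product are a real effect of the regimen, not bias. Controls use a study soap and can report reactions to it too.
- *The outcome will be under-counted.* The documents show only that it could be.

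It is also fair to say that section 2 states no tolerability objective; its secondary aim is quality of life. That lowers the stakes, but adverse effects remain a named outcome variable.

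**Conclusion.** The point holds in a limited form. Section 4f fits poorly with section 4a and with the outcome in section 7b: followed as written, it lets mild or expected reactions go unrecorded or be recorded inconsistently. This is a matter of the rule as stated, not merely of missing detail. Neither the direction of any difference between arms nor the size of any shortfall can be established from the documents.

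The conclusion assumes that the section 4f definition applies to the visit check, since no other is given, and that no unseen form or questionnaire already requires these reactions to be recorded. The change should be made, but it concerns the secondary outcome and does not threaten the primary comparison.

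**What to change.** Reconcile section 4f with sections 4a and 7b:

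- State in section 4f that reported reactions *will* be documented, in place of *may*.
- Remove importance or unusualness as a condition for recording. The investigator can still grade importance after the event is recorded.
- At Visits 2 and 3, ask both groups the same short list of the section 8 reactions and record presence, severity and date. If the questionnaires already contain these items, refer to them instead of duplicating them.
- In section 7c, state that counts and proportions will be reported by arm.

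The cost is some rewording and a short checklist at visits that already include an adverse event check. The reported event rate will probably be somewhat higher, partly because solicited questions bring out minor symptoms, and the report should say that events were solicited.

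### The between-group comparison is an unpaired t-test, most naturally on change, which uses the Visit 2 score inefficiently and states no variance form under about 3:1 allocation

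*Combined protocol and SAP*

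**What the plan says.** Section 7c is the whole statistical plan, and no separate SAP text supplements it. On method it states: "Analysis will include paired and unpaired t-tests with two-tailed p-values". On timing: "Values obtained at baseline, in middle of the study and after completing the study will be compared". On the group comparison: "The difference of measure values will be compared between application group and control group". It names no covariate or model, no pooled or Welch form, and no visits to be subtracted.

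Section 4a supplies the design. Up to 100 participants are assigned at random, about 75% to the regimen and 25% to control. Both groups go through the same one-week washout. Visit 2 is labelled as the baseline, and there the plan says "During this visit, investigators will perform clinical assessments, take photographs and administer subject questionnaires". The same assessments are repeated at Visit 3, on day 14±2. The covariate needed for an adjusted analysis is therefore already collected in both arms.

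**The concern.** At most about 25 controls carry the comparison, so precision is limited. A t-test on change does use the Visit 2 score, but it subtracts that score in full whatever the correlation between visits. When the correlation is modest, full subtraction adds noise that an estimated slope would avoid.

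The second point is an omission. An unpaired t-test may pool the two variances or keep them separate. With equal group sizes the choice hardly matters. At about 3:1 it does, because a pooled variance is dominated by the larger arm while the smaller arm contributes most of the uncertainty. Leaving the form unstated leaves the error rate to a software default or to a choice made after the data are seen.

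**Working it through.** **Inputs from the documents.** N is up to 100, split about 75/25 (section 4a); tests are two-sided t-tests (section 7c). The plan gives no alpha, power, SD, correlation or effect size, so it has no sample size figure to reproduce.

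**Assumptions.** Alpha 0.05, power 80%, SD of a single score 1 in both arms, no dropout, correlation rho between Visits 2 and 3 from 0.3 to 0.9, and the same slope in both arms.

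**Step 1: variance, equal SDs at both visits.** Change score: 2(1 − rho). ANCOVA: 1 − rho². Ratio: (1 + rho)/2.

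**Step 2: detectable difference at 75/25.** (1.960 + 0.842) × SD × √(1/75 + 1/25) = 0.647 × SD, where SD is the square root of the Step 1 variance.

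| rho | Change variance | ANCOVA variance | Ratio | Detectable, change | Detectable, ANCOVA |
|---|---|---|---|---|---|
| 0.3 | 1.40 | 0.91 | 0.65 | 0.77 | 0.62 |
| 0.5 | 1.00 | 0.75 | 0.75 | 0.65 | 0.56 |
| 0.7 | 0.60 | 0.51 | 0.85 | 0.50 | 0.46 |
| 0.9 | 0.20 | 0.19 | 0.95 | 0.29 | 0.28 |

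Estimating the slope costs a factor of about 1 + 1/96, or 1% of variance, at N = 100.

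**Step 3: unequal SDs at the two visits.** With k = Visit 3 SD / Visit 2 SD, the ratio is (1 − rho²)/(1 + 1/k² − 2·rho/k).

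| rho | k = 0.8 | k = 1.25 |
|---|---|---|
| 0.3 | 0.502 | 0.784 |
| 0.5 | 0.571 | 0.893 |
| 0.7 | 0.628 | 0.981 |
| 0.9 | 0.608 | 0.950 |

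The best slope is rho × k, so the gain vanishes where that product is near 1. At rho 0.7 and k = 1.25 it is 0.875, and only 2% is saved.

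**Step 4: power for an assumed 0.5 SD effect.** At rho 0.5, change gives 57% (noncentral t) and ANCOVA with HC3 errors about 67% (20,000 simulations). With ordinary ANCOVA errors the pairs, change versus ANCOVA, are 44% and 61% at rho 0.3, 57% and 69% at 0.5, 79% and 85% at 0.7, and above 99% for both at 0.9.

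**Step 5: the other reading.** If the t-test were on the Visit 3 score alone, its variance would be 1 against 1 − rho² for ANCOVA. That is a saving of rho², or 9% at rho 0.3 and 81% at rho 0.9. ANCOVA is more precise under either reading.

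**Step 6: variance form.** Two-sided type I error at 75/25, normal data, equal means. The t-tests use 400,000 simulations; ANCOVA uses 40,000 at rho 0.5.

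| Control/regimen SD ratio | Pooled t | Welch t | ANCOVA, ordinary errors | ANCOVA, HC3 |
|---|---|---|---|---|
| 0.8 | 2.9% | 5.1% | 2.9% | 4.7% |
| 1 | 5.0% | 5.0% | 5.0% | 4.8% |
| 1.25 | 7.9% | 5.1% | 7.9% | 4.9% |

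At 50/50 the pooled test stays at 5.0% to 5.1% for SD ratios from 0.5 to 2, so the 3:1 split is what makes the form matter. Moving to ANCOVA with ordinary errors would not cure this; robust errors do.

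**The case against.** A t-test on change is valid in a randomised two-arm study and already uses the Visit 2 score, so the ANCOVA point is one of efficiency. Its value depends on a correlation that the documents do not give, and at rho 0.9 it is negligible. That stands, and it limits the size of the point. It does not remove it, because the adjusted analysis needs no extra data and ANCOVA also improves on a t-test of the Visit 3 score alone.

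The type I error figures need a regimen that changes the spread of scores while leaving the mean unchanged. If the regimen does nothing to anyone, the arms share one distribution and the pooled test holds 5%. That also stands: the 2.9% and 7.9% describe a narrow case as false-positive rates. The same misstated standard error carries over to confidence intervals when a real effect exists. A shift in mean does not alter it, so a pooled 95% interval would cover 97.1% (100 − 2.9) or 92.1% (100 − 7.9). Welch is itself an unpaired t-test, so section 7c is incomplete here, not wrong.

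The plan's larger gap comes first: section 7a names no single score, and the baseline and middle time points in 7c do not map cleanly to the visit labels in 4a. That is fair, but the correction can be written for whichever score is chosen, and it settles the reference visit. Finally, 75/25 is the ceiling. Smaller enrolment or dropout enlarges every detectable difference, although the Step 1 and Step 3 ratios do not depend on N.

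**Conclusion.** The concern holds, as a loss of precision and an unstated variance form; the comparison is not biased. With equal SDs, ANCOVA on the Visit 2 score would cut the variance of the group difference by 5% to 35% over rho 0.9 to 0.3. With unequal visit SDs the saving ranges from 2% to 50%. At 75/25 and rho 0.5, the detectable difference falls from 0.65 to 0.56 SD. The variance form matters only if variances are pooled and the arms differ in spread. SD ratios of 0.8 and 1.25 then move a nominal 5% to 2.9% and 7.9%; larger distortions need larger ratios, which the documents neither support nor exclude.

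Rho, both sets of SD ratios and the 0.5 SD effect are assumptions. So is a common slope: if the slopes differed appreciably between arms, unequal allocation means that a gain from common-slope ANCOVA is not guaranteed. The recommendation to adjust does not depend on the variance-form point.

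**What to change.** In section 7c, make the between-group analysis an ANCOVA of the Visit 3 score on treatment group and Visit 2 (baseline) score, with heteroscedasticity-robust (HC3) standard errors. Report the adjusted difference with its 95% CI. State that Visit 2 is the reference visit, and apply the model to the score or scores that section 7a names as primary. If a t-test on change is kept as supportive, define change as Visit 3 minus Visit 2 and specify the Welch version.

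The cost is a wording change to the protocol, since the statistical plan sits in section 7c and not in a separate document. It requires no new data, visits or participants.
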